4.7.3. Relationship between Adverse Events and Investigational Vaccines

Impossible: Adverse events occur due to other factors, and there is sufficient evidence to prove that adverse reactions/events are caused by other reasons and have nothing to do with vaccination.

Unlikely: The occurrence of adverse events may be caused by other factors, such as the clinical status of the subject, other treatments or accompanying drugs, which are inconsistent with the known adverse reactions of vaccination.

Possible: Adverse events are consistent with known investigational vaccine information, have a reasonable temporal sequence with vaccination, and/or have occurred for vaccination. There is also a causal relationship with the investigational vaccine, but it may also be related to other factors.

Likely: Adverse events are consistent with the known investigational vaccine information and have causal relationship with the investigational vaccine, and cannot be explained by other factors, such as the clinical condition of the subject, other treatments or concomitant medication.

Definite: Adverse events are consistent with the known investigational vaccine information and have a causal relationship with the investigational vaccine, and this relationship cannot be explained by other factors, such as the clinical status of the subject, other treatments or accompanying drugs. In addition, adverse events occurred repeatedly when the subjects used the investigational vaccine again.

5. Selection and Withdrawal of Subjects

The subjects must fulfill all eligibility criteria to be involved in this study. No exemptions from any in-/exclusion criteria will be allowed. If any deviation from eligibility is retrospectively detected for an already randomized subject, the investigator and sponsor must decide immediately whether it is safe to treat this subject further within the study.

5.1. Study Population

5.1.1. Inclusion criteria

1. Healthy subjects aged 18 years old and above;
2. By asking for medical history and physical examination, the investigator judged that the health condition is well.
3. Female subjects of childbearing age were not pregnant at the time of enrolment (negative urine pregnancy test), were not nursing and had no family planning within the first 3 months after enrollment. Effective contraceptive measures have been taken within 2 weeks before enrolment;
4. During the whole follow-up period of the study, be able and willing to complete the whole prescribed research plan;
5. With self-ability to understand the study procedures, the informed consent & voluntarily

sign an informed consent form and be able to comply with the requirements of the protocol.

5.1.2. Exclusion Criteria for the first dose

1. Confirmed acute cases of SARS-CoV-2 infection;
2. With a medical history of SARS, MERS virus infection (self-report, on-site inquiry);
3. Fever (axillary temperature > 37.0 °C, tympanic temperature/temporal artery temperature > 37.5 °C), dry cough, fatigue, nasal obstruction, runny nose, pharyngeal pain, myalgia, diarrhea, shortness of breath and dyspnea within 14 days before vaccination;
4. Positive urine pregnancy test result;
5. Axillary temperature > 37.0 °C before vaccination (tympanic temperature/temporal artery temperature > 37.5 °C) ;
6. With previous severe allergic reactions (such as acute allergic reactions, urticaria, skin eczema, dyspnea, angioneurotic edema or abdominal pain) or allergy to known ingredients of the inactivated SARS-CoV-2 vaccine;
7. With a medical history or family history of convulsion, epilepsy, encephalopathy or mental illness;
8. With congenital malformation or developmental disorder, genetic defects, severe malnutrition, etc.;
9. With known or suspected diseases include acute respiratory diseases (e.g. influenza like illness, acute cough, sore throat), severe cardiovascular diseases, severe liver diseases, severe kidney diseases, uncontrollable hypertension (systolic blood pressure > 150 mmHg, diastolic blood pressure > 90 mmHg), diabetic complications, malignant tumors, various acute diseases, or acute attack period of chronic diseases.
10. Has been diagnosed with congenital or acquired immune deficiency, HIV infection, lymphoma, leukemia or other autoimmune diseases;
11. With a history of coagulation dysfunction (such as coagulation factor deficiency, coagulation disease);
12. Receiving anti-TB therapy;
13. Receiving immune enhancement or inhibitor therapy within 3 months (continuous oral or IV administration for more than 14 days);
14. Vaccinated live attenuated vaccine within 1 month before vaccination and other vaccines within 14 days before vaccination;
15. Received blood products within 3 months before vaccination;

16. Received other investigational drugs within 6 months before vaccination;
17. Other circumstances judged by investigators that were not suitable for participating in this clinical trial.

5.1.3. Exclusion criteria for the second dose of vaccine

1. Patients with high fever (axillary temperature ≥ 39.0 °C) lasting for 3 days after the previous dose of vaccine and severe allergic reaction;
2. Serious adverse reactions with causal relationship with the previous dose of vaccine;
3. Reach the endpoint of the study;
4. Urine pregnancy test positive;
5. for the subjects newly identified or with newly occurred symptoms which does not meet the inclusion criteria for the first dose or meets the exclusion criteria for the first dose after the previous dose of vaccine is vaccinated, the investigator shall determine whether they should continue to participate in the trial;
6. Other reasons for exclusion that investigator believes.

If any of the following occurs during the trial, the relevant subjects are not required to stop the trial:

- Non-specific immunoglobulins were used during the study;
- Continuous oral or IV administration of steroid hormones for 14 days.

5.1.4. Criteria for early withdrawal of subjects from trial

Subjects will be withdrawn from the trial in advance when any of the following conditions occur:

1. The subject or the subject's guardian requests to withdraw from the clinical trial;
2. Intolerable adverse events, whether related to test drugs;
3. The health status of the subjects does not allow them to continue to participate in this trial.
4. The subjects were vaccinated with other investigational vaccines during the study period.
5. Reach the endpoint of clinical trials;
6. Any other reason that the investigator believes.

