4.5. Vaccine efficacy

Research Indicators

$$\text{Vaccine efficacy} = \left(1 - \frac{\text{incidence density of vaccine group}}{\text{incidence density of placebo group}}\right) \times 100\%.$$

Incidence density during the follow-up period = (number of confirmed cases during the effective follow-up period/number of observation years of all vaccinated subjects during the effective follow-up period) × 100%. In the calculation of the number of observation years, the termination of follow-up period is considered as follows: for COVID-19 cases in the subjects, once there are confirmed cases that meet the diagnostic criteria of the "Diagnosis and Treatment Protocol for COVID-19" (the latest version), relevant data will be collected to complete follow-up; For non-cases, the follow-up of vaccine efficacy will be continued until the day of withdrawal from the study.

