7.4.8 Case Monitoring

This clinical trial adopts a monitoring modality with passive monitoring as the main approach and active monitoring as a supplement. After the subjects received the first dose of vaccine, the monitoring of COVID-19 cases will be initiated until the end of the study, and relevant information will be collected.

Passive Monitoring

Passive monitoring has two situations where subjects spontaneously report and when symptoms occur, they actively go to the hospital for treatment.

- 1) After the subjects develop symptoms, they actively report to the investigator through the hotline or email;
- 2) When the subjects visit hospital after developed symptoms, the subjects are monitored through hospital system;
 - When the subject has fever and/or respiratory symptoms that meet the definition of a suspected case, the subject should inform the investigator and go to the designated place for PCR testing;
 - If the subject visits the hospital for treatment, the investigator should arrange to collect nasopharyngeal swabs for PCR testing every 2-3 days; determine the clinical classification based on the severity and duration of symptoms, and isolate the mild and moderate cases; arrange hospitalization for severe and critical cases;
 - For non-hospitalized patients, the subjects will be followed up by remote teleconsultation and re-tested for PCR every 3 days to monitor and document the progress of the illness, medication status, symptom severity and other related information. If the subject's condition deteriorates, he needs to be sent to the hospital for timely treatment;
 - For hospitalized patients, continue to pay attention to the development of the disease, and conduct testing and examination like blood routine, blood chemistry, imaging examinations as well as other medical treatment. Closely monitor and collect evidence related to the subject's diagnosis and treatment, and record the progress of the disease, medication, and the severity of symptoms until the outcome;
 - Collect the PCR result, defined a confirmed case based on the positive result;
 - The subject is in the convalescent phase which is 3-4 weeks after the first positive PCR result. During the convalescent period, the subject's nasopharyngeal swab is collected for PCR retest

and neutralizing antibody test; if the PCR test result is positive, repeated PCR testing needs to be done once a week until the PCR result is negative.

2. Active monitoring

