Subjects need to be tested for COVID-19 RT-PCR before vaccination on D0, D21, D35 and D49, and once per two weeks after D49 at the site with conditions. Clinicians need to ask the subjects again in detail whether they have fever, dry cough, fatigue and other symptoms in the near future. If the above symptoms exist, the subjects are arranged to go to the agreement hospital for CT examination according to the protection requirements of COVID-19. If the examination results have CT imaging characteristics of COVID-19, samples are collected for etiological examination. If there are no symptoms such as fever, dry cough and fatigue, the subject should be home isolated under the arrangement of local CDC according to the requirements of COVID-19 prevention and control plan.

(4) Surveillance of disease process of COVID-19.

The purpose of monitoring the infection of COVID-19 or other coronaviruses in subjects is to find people with potential risks of ADE or VED after injection of COVID-19 vaccine, and to take timely treatment and intervention measures to reduce the risk of aggravation of patients' illness.

The responsible unit on the research site shall inform the medical institutions of the information on the subjects with COVID-19 vaccination, so as to assist doctors to make correct judgment on the patient's condition and potential risks. In addition to collecting nasopharyngeal swabs, alveolar fluid and serum samples of subjects for etiological detection of COVID-19, medical institutions also need to collect blood samples for antibody level detection. The responsible units and medical institutions on the research site should pay close attention to the progress of the subject's condition, and contact the superior medical or testing institutions which have capacity of testing IL-2, IL-6, IL-4, TNF- α , IFN- γ and other cytokines to get ready for sample delivery and testing. When the subject's condition progresses rapidly and has a tendency to ADE or VED, blood samples are collected and sent to a hospital or institution that can carry out the test to help diagnose whether ADE or VED exists.

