8.3. Handling and Reporting of Serious Adverse Events

Monitoring and reporting of adverse events in vaccine clinical trials are jointly completed by subjects, adverse event investigators, trial sites and responsible institutions at different observation time points with different stages.

The sponsor is the main body responsible for monitoring, evaluating and SAE reporting safety information of vaccine clinical trials. The person shall be designed as the administrator of clinical trial safety information monitoring and SAE reporting, and work with investigators to establish SOPs for clinical trial safety information monitoring and SAE reporting, know well the latest status of the safety information of the whole clinical trial, and timely report updates to all clinical trial institutions/ investigators and regulatory authorities.

If it is difficult to make a judgment on the correlation between SAE and vaccine or there is doubt about the judgment, when it is necessary to make a new judgment, the expert meeting shall make a judgment after argumentation.

(1) On-site treatment measures

Emergency plans for SAE treatment in clinical trials shall be established at the trial site, and all relevant personnel shall be trained. If the subjects show serious adverse events, the investigators shall immediately take appropriate measures for the subjects and record them. The investigators must take relevant approaches to know in time any clinically significant diseases/events related to vaccination. According to relevant national regulations, the subjects should be received appropriate treatment in time in the designated hospitals.

investigators at the trial site should follow up serious adverse events/reactions until the symptoms disappear or stabilize. The progress and outcome of all symptoms will be recorded in detail, and all drug treatments and medical treatments will be recorded at each follow-up. investigators should truthfully record serious adverse events on eCRF, which shall be evaluated and discussed in the final report after the test is completed or terminated.

During the whole observation process, if the subjects suffer from physical injuries caused by serious adverse reactions related to vaccination, which is confirmed by the expert investigation team, the sponsor will give corresponding compensation.

(2) Reporting Procedures for Serious Adverse Events

✓ Reporting Procedures of investigators

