Any serious adverse event, whether related to the investigational vaccine, the investigator must submit the first report of the "Serious Adverse Event Report Form" to the drug administration department, the sponsor and the ethics committee by fax, e-mail or EDC system or personal delivery within 24 hours after learning about it. Subsequently, the follow-up report of the "Serious Adverse Event Report Form" shall be submitted regularly until the end of the event. All information is reported in the "Serious Adverse Event Report Form" in the form of written reports, including description of adverse reactions/events, onset time and type, duration, intensity, causal

relationship with vaccination, results, treatment methods (symptomatic treatment) and other relevant clinical and laboratory data.

When receiving the report of serious adverse events/reactions, the researcher shall, together with the sponsor, comprehensively consider the duration, scope, intensity, outcome and the wishes of the subject to decide whether the subject should continue to participate in the test or terminate the test in advance.

✓ **the sponsor's reporting procedure**

During the clinical trial of drugs, sponsors need to quickly report unexpected and serious adverse reactions (SUSAR) that are definitely related to or suspicious of the tested drugs in the form of case-by-case safety reports according to the Standards and Procedures for Rapid Reporting of Safety Data during Clinical Trial of Drugs. If the researcher and the sponsor cannot reach an agreement on the judgment of the causal relationship between adverse events and drugs, either party's judgment cannot exclude those related to the test drugs, and the sponsor should also make a quick report.

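### Section 5.1.4 turns adverse events, ill health and receipt of another investigational vaccine into withdrawal from the trial rather than from vaccination, and no scheduled SAE or case contact is stated afterwards

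*Protocol*

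**What the plan says.** Protocol 5.1.4 opens with "Subjects will be withdrawn from the trial in advance when any of the following conditions occur". Item 2 is "Intolerable adverse events, whether related to test drugs". Item 3 is health status that does not allow continued participation, item 4 is vaccination with another investigational vaccine, and item 6 is any other reason the investigator holds. Items 1 (the subject's own request) and 5 (endpoint reached) are outside this point.

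Reasons to withhold dose 2 form a separate list in 5.1.3, for example "Serious adverse reactions with causal relationship with the previous dose of vaccine". That list does not itself end participation. It closes by naming two events (non-specific immunoglobulin, prolonged steroids) that do not require a subject to stop the trial. Adverse events are not among them.

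In defining observation years, section 4.5 says: "For non-cases, the follow-up of vaccine efficacy will be continued until the day of withdrawal from the study". Section 9.3 likewise ends person-time at the last follow-up date for non-cases.

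Some routes remain open after withdrawal. Under 8.3, "investigators at the trial site should follow up serious adverse events/reactions until the symptoms disappear or stabilize", and any SAE must be reported "within 24 hours after learning about it". Under 7.4.8, "When the subjects visit hospital after developed symptoms, the subjects are monitored through hospital system". Sections 4.4.3 and 8.2(5) state a 12-month SAE period, and 7.4.8 and Table 4 state case monitoring, for subjects in general. None says whether withdrawn subjects are covered.

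**The concern.** Stopping study vaccine and leaving the study are different decisions. Items 2 and 3, and item 6 when the reason is an adverse event or health, pick out people who have been or may have been harmed. For them the protocol provides leaving the trial and states no scheduled contact afterwards. After dose 2, withdrawal removes no further exposure. It can only remove observation.

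Three parts of the plan depend on that observation:

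- **SAE comparison.** The safety set (9.2) is everyone vaccinated after randomization. Section 9.3(5) compares SAE incidence within 360 days by chi-square or Fisher test, so a withdrawn subject stays in the denominator and unobserved time counts as event-free.
- **One-dose efficacy.** The FAS is said to follow the ITT principle and is used for VE after one dose. Subjects withdrawn after dose 1 stay in it, but their person-time stops.
- **Enhanced disease.** Section 8.2(4) says the purpose of monitoring infection "is to find people with potential risks of ADE or VED after injection of COVID-19 vaccine". Without scheduled monitoring, COVID-19 arising later in someone withdrawn for an adverse event or ill health could go unseen.

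A SAP can choose how to treat missing follow-up. It cannot recover data that were not collected.

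**Working it through.** The protocol has no figure of its own on this point to reproduce. The timing figures below use its schedule and hold **if** no contact takes place after withdrawal. The frequency figures are assumptions, because the protocol gives no rate for these withdrawals and no SAE rate.

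**1. Observation lost by one subject** (dose 2 at D21; last visit D381, Table 4)
- SAE comparison: D21 + 360 = D381. Withdrawn at D28, which is 7 days after dose 2: 360 − 7 = 353 days lost; 353/360 = 98%.
- Visits: 8 to 21 are lost, 14 of 21.
- Weekly case calls (Table 4, D0–D215): D7 to D210 gives 30 calls; D35 to D210, the calls lost, gives 26.
- FAS follow-up when withdrawn at D3, after one dose: 381 − 3 = 378 of 381 days.

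**2. Number of subjects** (15,000 per arm; assumed 0.1–1% withdrawn under these items)
- 0.001 × 15,000 = 15; 0.01 × 15,000 = 150.
- The 15% drop-off rate in 9.4.1 allows 0.15 × 15,000 = 2,250 per arm. So 15/2,250 = 0.7% and 150/2,250 = 6.7% of that allowance.

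**3. SAE comparison** (assumed new-SAE risk 0.5–2%)
- Missed per arm: 15 × 0.005 = 0.075 (about 0.08), up to 150 × 0.02 = 3.
- Expected per arm: 15,000 × 0.005 = 75, up to 15,000 × 0.02 = 300.
- Top of the range in one arm only: 300/15,000 = 2.00% against 297/15,000 = 1.98%, a shift of 0.02 percentage points. Fisher p = 0.93; uncorrected chi-square p = 0.90.

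**4. Primary efficacy person-time** (starts 14 days after dose 2, D35; 381 − 35 = 346 days at most)
- All 150 leave before D35: 150 × 346 / (15,000 × 346) = 1.00%.
- All 150 leave at D49: 381 − 49 = 332 days each; 150 × 332 / (15,000 × 346) = 0.96%.
- 1.00% of the 150 target cases is 1.5. Analyses are triggered at 50, 100 and 150 cases, so this is a slight delay rather than lost information provided the target is reached. For the same reason, 346 days is an upper limit.

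**The case against.** A reader might infer that 4.5 orders case surveillance to stop at withdrawal. The text does not support that. The sentence sits in the rule for counting observation years, so it defines person-time for the VE formula and does not instruct sites to stop calling. The general 12-month SAE and case-monitoring statements do not exclude withdrawn subjects either. What stands is narrower: 5.1.4 takes the subject out of the trial, and nothing says the scheduled contacts carry on. The losses in step 1 depend on sites reading it that way.

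A reader might also infer that every adverse event forces withdrawal. It does not. Item 2 turns on whether the event is intolerable, which is a judgement, as is item 6. After an SAE, 8.3 has the investigator and sponsor weigh the course of the event and the subject's wishes before deciding on continuation. That discretion is real, but the choice offered is to continue or to end early, with no option of stopping vaccine while staying in follow-up.

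Item 3 is defined by inability to take part, so it cannot simply become a vaccination stop on the full visit schedule. That objection is correct and shapes the fix. For item 4, ending efficacy person-time is right, and only SAE collection is at issue.

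The enhanced-disease argument has limited reach. A confirmed case leaves under item 5, so the argument concerns only subjects withdrawn before they become cases.

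The denominator problem affects every early leaver, and its analysis can be left to a SAP. Poisson person-time and Kaplan–Meier handle early exit by censoring, subject to the usual assumption that loss is not informative. Rewording 5.1.4 removes only the loss that the protocol itself creates.

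**Conclusion.** The point holds as a minor one. Section 5.1.4 makes adverse events, health reasons and another investigational vaccine grounds for leaving the trial rather than for stopping vaccination, even after dose 2, and the protocol states no scheduled SAE or case contact afterwards. Known SAEs remain covered by 8.3.

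A reader might go further and infer a biased SAE comparison or VE. The documents do not support this. At the top of the assumed ranges, with all loss in one arm, the SAE comparison does not move materially, and primary person-time falls by at most 1.00%. Those results rest on the assumed 0.1–1% withdrawal rate and 0.5–2% SAE risk, and the direction of any difference between arms is unknown. The gain from a change is safety follow-up and completeness in people selected for harm, not a different trial conclusion.

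**What to change.** In 5.1.4:
- Make items 2 and 4, and item 6 where the reason is an adverse event or health, grounds to stop further study vaccination only. State that, unless the subject withdraws consent, SAE contacts and case surveillance continue on the Table 4 schedule to D381.
- For item 4, record the date of the other vaccine and censor efficacy person-time there, while SAE collection continues.
- Reword item 3 to health status that does not allow further study vaccination, and permit telephone-only SAE and case contact when visits are not feasible. Section 8.2(5) already uses the telephone for long-term safety.

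Align the end of follow-up in 4.5 and the continuation decision after an SAE in 8.3, adding the option of follow-up without further vaccine. Who should be refused dose 2 is a separate clinical decision and is left as it is.

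The cost is wording in three sections and a small number of extra subjects to follow. The protocol does not quantify that number; it is 15–150 per arm under the assumed rates. The contacts are those already scheduled.

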3.3. Exploratory Study

Explore the anti-SARS-CoV-2 neutralizing antibody protective level after 14 days following 2-dose immunization (immunological surrogate endpoint).

The occurrence of ADE/VED after immunization.

4. Trial Design and Description

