4.4.3. Safety Endpoint

The incidence of adverse reactions/events within 30 minutes after each dose of vaccination.

The incidence of solicited and unsolicited adverse reactions/events within D0 ~ 7, and unsolicited events and SAEs within D8 ~ 21/28 after each dose of vaccination.

The incidence of serious adverse events (SAE) from the first dose of vaccination to 12 months after the last dose of vaccination.

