- 1) Weekly teleconsultation to collect information;
- 2) Regularly monitor and collect information;

The subsequent procedures for suspected cases identified through the above two monitoring process approaches is the same as passive monitoring procedures.

Endpoint assessment or adjudication of the cases

Establish an independent case Endpoint Assessment or Adjudication Committee (EAC) composed of 3 or more local medical experts to make a final diagnosis for each case. When a case meets the etiological indicators, the diagnosis and treatment progress document, case investigation document, serology, cytokines and other lab reports will be submitted to EAC, the case can be determined as a confirmed case of COVID-19 (clinical endpoint) after a blinded review of the EAC experts. Refer to the EAC charter (Appendix 1) for details.

Case Monitoring Flowchart

[figure not shown]

Table 4. Schedule of Events

Visit number	1	2	3	4	5	6	7	8	9	10	11, 13, 14	12, 15, 18	16, 17, 19, 20	21
Day (safety visit)	D0 ☞	D3 ☞	D7 ☞	D14 ☞	D21 ☞	D24 ☞	D28 ☞	D35 ☞	D42 ☞	D49 ☞	D81 D141 D171 ☞	D111(M3) D201 (M6) ; D291 (M9) ☞	D231 D261 D321 D351 ☞	D381 (M12) ☞
Visit (window +/- days)	0d	-2d	+2d	+3d	+7d	-2d compare to V5	+2d compare to V5	+10d compare to V5	+3d compare to V5	+10d compare to V7	+3d compare to V7	+10d compare to V7	+3d compare to V7	+10d compare to V7
SCREENING/BASELINE														
Study Informed consent ¹	✓													
Inclusion/exclusion criteria evaluation	✓ ⁷				✓ ⁷									
Demographics	✓													
Medication history	✓				✓									
Measured height	✓				✓									
Review contraception ²	✓				✓									
EDC Randomization registry	✓													
TREATMENT														
Administer study drug	✓				✓									
SAFETY ASSESSMENTS														
Vital signs specifically RR, HR, BP, body temp/ O2 sat	✓				✓			✓		✓				
Body weight	✓				✓									
Physical Examination ⁶	✓ ⁶				✓ ⁶			✓ ⁶		✓ ⁶				
Post-vaccination observation at site ⁴	✓				✓									
Post-vaccination phone call	✓	✓	✓	✓	✓	✓	✓	✓	✓	✓	✓	✓	✓	✓
Concomitant medication	✓	✓	✓	✓	✓	✓	✓	✓	✓	✓	✓	✓	✓	✓
Adverse events	✓	✓	✓	✓	✓	✓	✓	✓	✓	✓	✓	✓	✓	✓
Diary Card ⁵	✓				✓					✓				
LABORATORY TESTING														
COVID-19 PCR ⁷	✓							✓ ⁷						
Pregnancy test	✓ ³				✓ ³									
Neutralizing Antibody Test	✓							✓		✓ ⁸		✓ ⁸		✓ ⁸

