After unblinding, if the subjects in the experimental group suffer from diseases caused by COVID-19 again, and the disease progresses rapidly, indicating the high probability of ADE or VED. Doctors should be advised to take immune intervention measures to prevent inflammatory storms, or to transfer to a superior hospital in time to prevent more serious injuries due to improper treatment.

(5) Persistent monitoring and long-term safety follow-up of COVID-19 antibodies

According to the requirements of the protocol, the subjects are followed up for a long-term safety period of 12 months, during which serious adverse event information, including disease information caused by COVID-19, is collected through telephone follow-up and active report by the subjects.

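### Protocol 5.1.4 withdraws subjects from the trial once they reach the endpoint, which contradicts the 12-month SAE follow-up and the ADE/VED surveillance promised elsewhere

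*Protocol*

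**What the plan says.** Section 5.1.4 opens with a mandatory rule: "Subjects will be withdrawn from the trial in advance when any of the following conditions occur". Item 5 of its list is "Reach the endpoint of clinical trials"; item 2 is an intolerable adverse event, related to the product or not. The section does not say which endpoint is meant, and it does not separate leaving the trial from ending efficacy observation.

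Other sections bear on the meaning and the consequences:

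- **7.4.8** uses the word endpoint for an adjudicated case: "the case can be determined as a confirmed case of COVID-19 (clinical endpoint) after a blinded review of the EAC experts".
- **5.1.3** has its own list of reasons to withhold the second dose, one of which is "Reach the endpoint of the study".
- **4.4.3** sets as a safety endpoint "The incidence of serious adverse events (SAE) from the first dose of vaccination to 12 months after the last dose of vaccination", with no exception for subjects who become cases.
- **8.2(5)** says that "the subjects are followed up for a long-term safety period of 12 months", and includes COVID-19 illness in the information to be collected.
- **3.3** lists as an exploratory objective "The occurrence of ADE/VED after immunization". **8.2(4)** treats rapid progression in a vaccinated subject who falls ill with COVID-19 again after unblinding as a strong pointer to ADE or VED.
- **7.4.8, Table 4 and 8.3** follow hospitalized cases to their outcome, visit suspected cases until recovery, retest PCR and antibodies 3 to 4 weeks after the first positive PCR, and follow SAEs until they resolve or stabilize.

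**The concern.** A subject withdrawn from the trial is no longer a source of trial data. If a confirmed case triggers withdrawal, the 12-month SAE endpoint cannot be observed in the cases, and a second COVID-19 episode cannot be observed at all. Enhanced disease can show itself only in vaccinated subjects who become infected, and these would be among the subjects leaving.

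The removal also depends on outcome. If a vaccine works, more placebo subjects become cases, so more placebo subjects leave. A site that applies 5.1.4 literally and a site that follows 7.4.8 and 8.2 would collect different data on the same kind of subject, and nothing in the protocol says which section prevails.

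Item 2 raises the same conflict: it removes from the trial subjects whose safety course 4.4.3 and 8.3 require to be recorded.

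**Working it through.** **What does endpoint mean in 5.1.4?**

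1. Reaching the end of the study does not fit, because the lead-in concerns leaving the trial ahead of time.
2. Merely stopping vaccination does not fit well either. Second-dose exclusions have their own section, 5.1.3. The primary endpoint (4.4.1) counts cases only from 14 days after dose 2, when no dose remains to be withheld.
3. Section 7.4.8 applies the label clinical endpoint to an adjudicated COVID-19 case. This is the only place that ties the word to an event in an individual subject.

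The COVID-19 reading is therefore the most natural one, but it is an inference.

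**What would be lost?**

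| Data on a confirmed case | Required by | Under 5.1.4(5) as written |
|---|---|---|
| Index episode to outcome, convalescent retest | 7.4.8, Table 4, 8.3 | Contradicted, but explicitly scheduled |
| SAEs after the episode, to month 12 | 4.4.3, 8.2(5) | Contradicted; no case procedure secures it |
| Late deterioration or death after the episode | 4.4.3, 8.2(5) | Contradicted; no case procedure secures it |
| Repeat COVID-19 and its severity | 8.2(4) | Contradicted; no case procedure secures it |

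**How many subjects?**

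Inputs from 9.4.1: 150 cases per vaccine-placebo pair, efficacy (VE) 0.6, placebo annual incidence 0.0085, 15% drop-off, 15,000 per arm, allocation 1:1:1.

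The plan's own figures reproduce:

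- N per group = 150 / [(1 + 1 − 0.6) × 0.0085] = 12,605
- Total = 12,605 / 0.85 × 3 = 44,488

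With equal arms, the expected placebo share of cases is 1/(2 − VE) and the vaccine share is (1 − VE)/(2 − VE):

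| VE | Placebo cases | Vaccine cases | Ratio | Share of 15,000 per arm |
|---|---|---|---|---|
| 0.30 | 88 | 62 | 1.4 to 1 | 0.59% v 0.41% |
| 0.50 | 100 | 50 | 2 to 1 | 0.67% v 0.33% |
| 0.60 | 107 | 43 | 2.5 to 1 | 0.71% v 0.29% |
| 0.76 | 121 | 29 | 4.2 to 1 | 0.81% v 0.19% |

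The values 0.30 and 0.50 are the protocol's success criteria; 0.76 is the point estimate that the synopsis attaches to the first interim boundary.

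**How much safety person-time?** Assume that cases arise evenly over one year, so that a case loses half a year on average:

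- Placebo: 0.0085 / 2 = 0.43%
- Vaccine: 0.0085 × 0.4 / 2 = 0.17%
- Difference: about 0.26 percentage points, against a planned drop-off of 15%

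**Effect on the primary analysis.** None. Section 9.3 already ends a case's person-time at diagnosis, so N and the 150-case target stay as they are.

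**The case against.** The strongest reply is that 5.1.4(5) is one loosely translated list item set against several detailed operating instructions. Sections 7.4.7, 7.4.8, 8.2(4) and 8.3 and Table 4 describe at length how cases are tested, visited and followed. Under 7.4.8, a case becomes the clinical endpoint only after the committee has reviewed its disease-course documents, so much of the episode would be on file before the withdrawal rule could apply. This stands for the index episode. It does not reach the months after convalescence, for which no case procedure exists and only the general 12-month follow-up applies.

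A second reply is that 5.1.3 does not prove the COVID-19 reading. That is correct: the two sections word the condition differently, and no one can meet the primary endpoint before dose 2. The reading rests on 7.4.8.

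Some stronger conclusions that a reader might draw are not supported:

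- **Severe-disease follow-up is cut off.** It is not. The case procedures explicitly keep the index episode under observation, so on that part the fault is an unresolved contradiction.
- **Section 4.5 also ends safety follow-up.** Its phrase "relevant data will be collected to complete follow-up" belongs to the calculation of observation years for efficacy. It fixes when efficacy person-time stops and says nothing about SAEs.
- **The whole population at risk of ADE/VED is lost.** Placebo cases received no antigen and serve as comparators. Infected subjects who are not confirmed cases, such as those without symptoms, would not be withdrawn under item 5.
- **The 12-month SAE comparison is materially biased.** With under 1% of each arm affected, it cannot be.

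**Conclusion.** The contradiction is real. Read with 7.4.8, section 5.1.4(5) removes confirmed cases from a trial that elsewhere promises to follow every subject for SAEs to 12 months after the last dose and to watch for enhanced disease on repeat illness. No section reconciles the two.

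The exposure is limited to SAEs after the episode, late deterioration or death, and repeat COVID-19, in about 107 placebo and 43 vaccine subjects per comparison. The imbalance is 2.5 to 1 at the assumed efficacy and ranges from 1.4 to 1 (VE 30%) to 4.2 to 1 (VE 76%). Overall SAE rates would scarcely change. The loss matters because it is concentrated in the subjects who inform the ADE/VED objective.

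This rests on three assumptions: that endpoint means a committee-confirmed COVID-19 case, that sites apply 5.1.4 as written, and that 150 cases accrue at the planning values. Confirmed cases before day 14 after dose 2 would add to the count. The change should be made, although it does not threaten the primary result.

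**What to change.** Amend 5.1.4 so that it agrees with 4.4.3, 7.4.8 and 8.2:

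- Define endpoint in item 5.
- State that a confirmed case ends that subject's person-time for the primary endpoint only, as 4.5 and 9.3 already provide for the analysis.
- State that data collection on SAEs, disease course and ADE/VED continues to month 12 unless the subject withdraws consent.
- Reconcile item 2 with 4.4.3 and 8.3 in the same way, for data follow-up only.

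This point takes no position on dosing or clinical management; the second-dose rules in 5.1.3 are outside it.

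The cost is amendment wording and continued contact with about 150 subjects per comparison, which the visit schedule and 4.4.3 already foresee. The sample size, the 150-case target and the primary analysis do not change.
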